4.4. Concomitant Medications and Procedures

Current concomitant medications are recorded in the study database at enrollment. Concomitant medications are updated in the study database if there is an occurrence of an adverse event (AE) that requires expedited reporting. If it will not endanger a subject's health, non-investigational vaccines should not be administered 14 days before or until at least 28 days after a study injection. Licensed vaccines received by the subject within 4 weeks before the first study injection administration and 4 weeks after last study injection will be recorded in the study database. Otherwise, a record of concomitant medication changes throughout the study will not be recorded in the study database.

4.5. Criteria for Discontinuing Subject Participation

4.5.1. Discontinuation of Study Injections

A subject may be discontinued from receiving study injections for the following reasons:

- Pregnancy;

- Grade 3 AE assessed as related to a study injection (with the exception that self-limited Grade 3 solicited reactogenicity does not require discontinuation of study injections);
- Grade 4 AE assessed as related to a study injection;
- Immediate hypersensitivity reaction associated with a study injection;
- CHIKV infection or other intercurrent illness that is not expected to resolve prior to the scheduled study injection assessed by study clinician to require withdrawal from the injection schedule;
- Treatment with systemic glucocorticoids (e.g., prednisone or other glucocorticoid) or other immunomodulators (other than nonsteroidal anti-inflammatory drugs [NSAIDs]), with the exception that, study injection may continue per investigator discretion if the next one occurs at least 2 weeks following completion of glucocorticoid treatment;
- The study PI assesses that it is not in the best interest of the subject to continue on the injection schedule.

4.5.2. Discontinuation from Protocol Participation

A subject may be discontinued from protocol participation for the following reasons:

- Subject voluntarily withdraws;
- Subject develops a medical condition that is a contraindication to continuing study participation;
- The Investigational New Drug (IND) sponsor or regulatory authorities stop the protocol;
- The study PI assesses that it is not in the best interest of the subject to continue participation in the study or that the subject's compliance with the study is not sufficient.

4.6. Criteria for Pausing the Study

The IoR for each site and IND sponsor will closely monitor and analyze study data as they become available and will make determinations regarding the presence and severity of AEs. The administration of study injections and new enrollments will be paused and the IND Sponsor will be promptly notified according to the following criteria:

One (or more) subject experience a **SAE** assessed by the IND Sponsor as related to study injection.

Two (or more) subjects experience the same **Grade 4** unsolicited AE assessed by the IND Sponsor as related to the study injection.

Plan for Review of Pauses and Resuming Rules:

The IND Sponsor, with participation by the PSRT, will consult with the DSMB to conduct the review and make the decision to resume or close the study. As part of the pause review, the

reviewers will also advise on whether the study needs to be paused again for any subsequent AEs of the same type.

The study injections and enrollments would resume only if review of the AEs that caused the pause resulted in a recommendation to permit further study injections and study enrollments. When indicated, safety data reports and changes in study status will be submitted to relevant regulatory authorities including the IRB in accordance with [Section 5.4](#) and institutional policy.

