4.2.4. Administration of Injections

All Day 0 injections will be administered in a blinded manner according to the randomization assignment. Neither the clinic staff nor the subjects will know whether the injection is VRC-CHKVLP059-00-VP or PBS placebo.

Prior to the first study injection, staff should recheck eligibility to ensure the volunteer is still eligible.

Before each injection, clinic staff must collect research and safety blood and vital signs on the subject.

All injections will be administered IM into the upper arm deltoid muscle by needle and syringe. It is recommended, but not required, to administer the first injection into the non-dominant arm and to alternate arms for the second injection. When choosing an arm for the injection, clinicians should consider whether there is an arm injury, local skin problem or significant tattoo that precludes administering the injection or that will interfere with evaluating the arm after injection.

Following the study injection, the subject will remain in the clinic for observation for at least 15 minutes. After 15 minutes, blood pressure and pulse will be taken and the injection site will be inspected for evidence of local reaction before the subject leaves the clinic. In keeping with good medical practice, acute medical care will be provided to subjects for any immediate reactions to a study injection.

4.2.5. 7-Day Diary Card and Follow-Up

Subjects will be given a “Diary Card” to use as a memory aid, on which to record the solicited signs and symptoms daily for 7 days following each injection. If the solicited parameters are recorded directly by the subject through an electronic database, the subject’s electronic record will be the source for these data. The site may use a paper diary card as a source document or clinician notes obtained by telephone interview as the source for the information recorded in the study database. The solicited signs and symptoms on the diary card will include the following parameters: pain/tenderness at injection site, largest diameters of redness (erythema) and swelling (induration at injection site, highest measured temperature per day, unusually tired/feeling unwell, muscles aches (other than at injection site), arthralgia (joint pain), headache, chills, and nausea.

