At least one contact at about 7 days after each study injection will be conducted to complete the review of solicited diary card information. Subjects will be asked to contact the clinic at any time following each injection if they have any concerning signs or symptoms. Events that will require clinical evaluation include rash, urticaria, arthralgia, fever of 38.5°C (Grade 2) or higher lasting greater than 24 hours, or significant impairment in the activities of daily living. Additionally, other clinical concerns may prompt a study visit based on the judgment of a study clinician.

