5.1.2. Adverse Event Reporting in the Study Database

The following guidelines will be used to determine whether or not an AE is recorded in the study database.

Each AE will be graded according to the table for grading severity of AEs (see [Appendix IV](#)).

Solicited AEs will be recorded in the study database separately with data collection for 7 days after both the first and second study injections as detailed in [Section 4.2.4](#); without the collection of attribution assessments. All unsolicited AEs will be recorded in the study database from receipt of first study injection through 4 weeks after the last study injection administered. At subsequent follow-up visits, only SAEs (as defined in [Section 5.2](#)), new chronic medical conditions, and CHIKV cases will be recorded through the last study visit. Laboratory confirmed cases of CHIKV will be recorded on a CHIKV endpoints form rather than on an AE form without an attribution assessment.

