5.2. Serious Adverse Events

5.2.1. Serious Adverse Event Definition

The term “Serious Adverse Event” (SAE) is defined in the 21 CFR 312.32 in terms of the following outcomes: Death, a life-threatening AE, inpatient hospitalization or prolongation of existing hospitalization, a persistent or significant incapacity or substantial disruption of the ability to conduct normal life functions, or a congenital anomaly/birth defect. Important medical events that may not result in death, be life-threatening, or require hospitalization may be considered serious when, based upon appropriate medical judgment, they may jeopardize the patient or subject and may require medical or surgical intervention to prevent one of the outcomes listed in this definition. Examples of such medical events include allergic bronchospasm requiring intensive treatment in an emergency room or at home, blood dyscrasias

or convulsions that do not result in inpatient hospitalization, or the development of drug dependency or drug abuse.”

An SAE will be considered "life-threatening" if, in the view of either the investigator or sponsor, its occurrence places the patient or subject at immediate risk of death. It does not include an AE or suspected adverse reaction that, had it occurred in a more severe form, might have caused death.

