5.2.2. Reporting Serious Adverse Events to the IND Sponsor

AEs that meet SAE Reporting Requirements must be reported and submitted by the clinical site on an expedited basis to the IND Sponsor, VRC, NIAID, NIH, according to sponsor guidelines as follows:

- death
- life-threatening
- results in persistent or significant disability/incapacity
- requires unplanned inpatient hospitalization or prolongation of existing hospitalization
- is a congenital anomaly/birth defect in the offspring of a study subject
- is an important medical event that may jeopardize the patient or may require intervention to prevent one of the other outcomes listed above

In addition, any event, regardless of severity, which in the judgment of a site investigator represents a serious AE, may be reported on an expedited basis.

A site investigator will communicate an initial SAE report within 3 days of site awareness of occurrence to VRC (IND Sponsor) through the communication methods provided by the CRO.

Any SAE entered into the study database will generate automatic email notification to the VRC Medical Officer. This email notification and/or a written report by the study site will be sent to the attention of [contact] within 3 working days in order for the sponsor to comply with regulations mandating sponsor notification of expedited SAEs to the U.S. FDA.

The investigator must submit additional information as it becomes available. Personal identifying information about the subject will be removed by the site from SAE case reports before submission to the IND Sponsor.

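### The Grade 4 pause criterion in protocol Section 4.6 counts only unsolicited events, so fever above 40 °C in the 7 days after an injection can never meet it

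*Combined protocol and SAP*

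**What the plan says.** Protocol Section 4.6 has two criteria for pausing. The first is one or more SAEs that the IND Sponsor judges related. The second is two or more subjects with the same Grade 4 "unsolicited AE assessed by the IND Sponsor as related to the study injection".

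The diary card in Section 4.2.5 solicits ten items for 7 days after each injection, among them "highest measured temperature per day". The Appendix IV vital-signs table places fever above 40 °C (104 °F) in the Grade 4 column, with no requirement for hospitalization or treatment. Section 5.1.2 records solicited events separately, "without the collection of attribution assessments", and records unsolicited AEs from the first injection until 4 weeks after the last.

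Two other provisions bear on the point. Section 4.5.1 lists reasons why one subject's injections may be stopped. Its solicited exemption is that "self-limited Grade 3 solicited reactogenicity does not require discontinuation of study injections"; its next bullet, "Grade 4 AE assessed as related to a study injection", has no solicited exemption. Section 5.2.1 treats an event as life-threatening if, "in the view of either the investigator or sponsor, its occurrence places the patient or subject at immediate risk of death", and Section 5.2.2 also requires reporting of an event that "is an important medical event that may jeopardize the patient or may require intervention to prevent one of the other outcomes listed above".

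**The concern.** A two-subject Grade 4 rule protects the remaining participants from a severe reaction that repeats. The week after injection is when a febrile reaction to a vaccine is most plausible, and that is the week the second criterion leaves out for fever. A related fever above 40 °C on day 10 counts toward the pause; the same fever on day 1 does not.

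What is at stake is participant safety. Two related fevers of this grade could end the injections of those two subjects under 4.5.1 while no Grade 4 pause criterion is met for anyone else. Because attribution is not collected for solicited events, the relatedness judgment that the criterion depends on would not routinely be on record either.

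**Working it through.** **Which solicited events are affected.** The ten diary items were set against the Grade 4 definitions in Appendix IV.

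- Seven (pain/tenderness, tiredness/feeling unwell, muscle aches, arthralgia, headache, chills, nausea) reach Grade 4 only through hospitalization. Arthralgia and chills have no row of their own and take the general systemic-illness row. A hospitalized case is an SAE, so one related case meets the first criterion.
- Two (redness, swelling) need necrosis or, for redness, exfoliative dermatitis, requiring medical attention. Either could be recorded as an unsolicited AE in its own right.
- One (temperature) reaches Grade 4 on a measurement alone.

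The gap is therefore mainly non-hospitalized fever above 40 °C within 7 days of an injection.

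**Whether the first criterion covers it.** Only if a case is judged to carry an immediate risk of death, or is reported as an important medical event, and the sponsor then judges it related. A reading above 40 °C meets neither description automatically.

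**Plan's own figure.** The documents state no operating characteristic for the pause rule. As a check on method, the nearest stated figure is the 0.10% row of protocol Table 3 (n = 180): 1 − 0.999^180 = 16.48%, which agrees.

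**Chance that the amended criterion would be met.** The documents give no rate for fever above 40 °C. The rates p below are assumptions, defined per subject over both 7-day windows. The group sizes, 200 vaccinees and 400 subjects in all, are those of the Précis.

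P(2 or more) = 1 − (1 − p)^n − n·p·(1 − p)^(n − 1)

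Vaccine-related fever, n = 200, all judged related:

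- p = 0.05%: 1 − 0.90481 − 0.09053 = 0.0047 (0.5%)
- p = 0.1%: 1 − 0.81865 − 0.16389 = 0.0175 (1.746% before rounding, so 1.7%)
- p = 0.25%: 1 − 0.60615 − 0.30384 = 0.0900 (9.0%)

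Background fever unconnected with the vaccine, n = 400, before any relatedness judgment:

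- p = 0.05%: 1 − 0.81869 − 0.16382 = 0.0175 (1.749% before rounding, so 1.7%)
- p = 0.1%: 1 − 0.67019 − 0.26834 = 0.0615 (6.147% before rounding, so 6.1%)
- p = 0.25%: 1 − 0.36742 − 0.36834 = 0.2642 (26%)

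As written, the chance that the second criterion is met by these solicited fevers is zero at every rate.

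**What Phase 1 adds.** Sections 1.3 and 8.5.2 report no fever among 25 subjects, 10 of them at 20 mcg. The one-sided 95% upper limit for any fever is 1 − 0.05^(1/25) = 11.3%. This points to a rare event but cannot exclude rates in the range above.

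**The case against.** The strongest reply is that this is a deliberate choice. Pause rules often leave out expected reactogenicity, and a dangerous fever can already pause the trial at one case through the first criterion, which is stricter than a two-subject rule. Detection does not depend on goodwill: clinical evaluation is required for "fever of 38.5°C (Grade 2) or higher lasting greater than 24 hours", daily site review is an assigned duty, and the PSRT reviews weekly until 4 weeks after the last injections (8.8.1). Participants live in chikungunya-endemic areas, where high fever has other causes, and relatedness would be judged under blinding. On equal assumed rates, the chance of a background-triggered pause is about three to four times the chance of a vaccine-triggered one (1.749/0.466 = 3.8; 6.147/1.746 = 3.5; 26.42/9.00 = 2.9).

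Much of this stands. The reviews are mandatory, and only the decision to pause is discretionary. Leaving out solicited reactions is reasonable at lower grades. The ratio is fair as arithmetic, but it compares a reversible pause, counted before the sponsor has excluded any fever with another explanation, with a pause prompted by a real vaccine effect.

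A reader might also infer that 4.5.1 and 4.6 contradict each other. They do not. Section 4.5.1 is permissive and concerns one subject, while 4.6 halts the whole trial, and a narrower trigger for the trial is normal. What 4.5.1 shows is only that Grade 4 solicited events are not treated as exempt elsewhere in the protocol. Nothing in the documents explains why a related fever above 40 °C should count on day 10 and not on day 1.

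**Conclusion.** The point holds in a narrow form and is minor. The second criterion in 4.6 cannot be met by solicited fever above 40 °C in any number of subjects. A pause would rest on a case being judged an SAE, or on a discretionary decision by the sponsor, PSRT or DSMB.

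The documents do not support the broader inference that severe solicited reactions as a class escape the pause rules, or that such fevers would go unreviewed. Seven of the ten diary items reach Grade 4 only through hospitalization and so fall under the first criterion, and the review of safety data is compulsory.

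At the assumed vaccine-related rates of 0.05%, 0.1% and 0.25%, the situation would arise with probability 0.5%, 1.7% and 9.0%. These figures assume independent subjects, all 200 vaccinees followed through both diary periods, and every vaccine-caused fever judged related. No incidence is claimed. The reading of the text does not depend on the rates.

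**What to change.** In Section 4.6, reword the second criterion to cover two or more subjects with *the same Grade 4 AE, solicited or unsolicited, assessed by the IND Sponsor as related*. In Section 5.1.2, add that the IND Sponsor's relatedness assessment is documented for any Grade 4 solicited event. Both edits are needed: the first depends on a judgment that the database does not now collect for solicited events.

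The cost is one phrase, one sentence and a relatedness record for a rare event, plus an occasional pause that can be lifted. At the assumed background rates, the 1.7%, 6.1% and 26% in 400 subjects should be read as the upper bound on that risk. The sponsor's judgment can remove fevers explained by another infection, but no particular reduction should be counted on, because Appendix IV maps possibly related events to related in two-category reports. Section 4.6 already asks the reviewers of a pause to advise whether later events of the same type need another one, which limits repeat pauses.

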5. SAFETY AND ADVERSE EVENTS

5.1. Adverse Events

5.1.1. Adverse Event Definition

An adverse event (AE) is any untoward or unfavorable medical occurrence in a human subject, including any abnormal sign (e.g., abnormal physical exam or laboratory finding), symptom, or disease temporally associated with the use of study treatment, whether or not considered related to the study treatment.

5.1.2. Adverse Event Reporting in the Study Database

The following guidelines will be used to determine whether or not an AE is recorded in the study database.

Each AE will be graded according to the table for grading severity of AEs (see [Appendix IV](#)).

Solicited AEs will be recorded in the study database separately with data collection for 7 days after both the first and second study injections as detailed in [Section 4.2.4](#); without the collection of attribution assessments. All unsolicited AEs will be recorded in the study database from receipt of first study injection through 4 weeks after the last study injection administered. At subsequent follow-up visits, only SAEs (as defined in [Section 5.2](#)), new chronic medical conditions, and CHIKV cases will be recorded through the last study visit. Laboratory confirmed cases of CHIKV will be recorded on a CHIKV endpoints form rather than on an AE form without an attribution assessment.

5.2. Serious Adverse Events

5.2.1. Serious Adverse Event Definition

The term “Serious Adverse Event” (SAE) is defined in the 21 CFR 312.32 in terms of the following outcomes: Death, a life-threatening AE, inpatient hospitalization or prolongation of existing hospitalization, a persistent or significant incapacity or substantial disruption of the ability to conduct normal life functions, or a congenital anomaly/birth defect. Important medical events that may not result in death, be life-threatening, or require hospitalization may be considered serious when, based upon appropriate medical judgment, they may jeopardize the patient or subject and may require medical or surgical intervention to prevent one of the outcomes listed in this definition. Examples of such medical events include allergic bronchospasm requiring intensive treatment in an emergency room or at home, blood dyscrasias

or convulsions that do not result in inpatient hospitalization, or the development of drug dependency or drug abuse.”

An SAE will be considered "life-threatening" if, in the view of either the investigator or sponsor, its occurrence places the patient or subject at immediate risk of death. It does not include an AE or suspected adverse reaction that, had it occurred in a more severe form, might have caused death.

5.2.2. Reporting Serious Adverse Events to the IND Sponsor

AEs that meet SAE Reporting Requirements must be reported and submitted by the clinical site on an expedited basis to the IND Sponsor, VRC, NIAID, NIH, according to sponsor guidelines as follows:

- death
- life-threatening
- results in persistent or significant disability/incapacity
- requires unplanned inpatient hospitalization or prolongation of existing hospitalization
- is a congenital anomaly/birth defect in the offspring of a study subject
- is an important medical event that may jeopardize the patient or may require intervention to prevent one of the other outcomes listed above

In addition, any event, regardless of severity, which in the judgment of a site investigator represents a serious AE, may be reported on an expedited basis.

A site investigator will communicate an initial SAE report within 3 days of site awareness of occurrence to VRC (IND Sponsor) through the communication methods provided by the CRO.

Any SAE entered into the study database will generate automatic email notification to the VRC Medical Officer. This email notification and/or a written report by the study site will be sent to the attention of [contact] within 3 working days in order for the sponsor to comply with regulations mandating sponsor notification of expedited SAEs to the U.S. FDA.

The investigator must submit additional information as it becomes available. Personal identifying information about the subject will be removed by the site from SAE case reports before submission to the IND Sponsor.

5.2.2.1 Regulations Applicable to the French Study Sites Only

This section applies only to sites in Martinique and Guadeloupe who follow regulatory oversight by the French National Agency for Medicines and Health Products Safety (ANSM).

A site investigator will communicate an initial SAE report within 24 hours of site awareness of occurrence to:

- VRC (IND Sponsor) through the communication methods provided by the IND Sponsor, and

- The legal representative of the sponsor in the European Union (EU) through the communication method provided by him/her.

